## **1.3** Rationale for the Study

With the increased availability of next-generation sequencing, oncologists are beginning to incorporate genomic profiling into the routine care of cancer patients. More than half of all patients will have an actionable genomic alteration in their tumor when profiled, which could help guide the choice of targeted therapy treatment. Multiple targeted agents are now available

CONFIDENTIAL	
STUDY DRUG(S): REGORAFENIB/AFATINIB/CABOZANTINIB	SARAH CANNON DEVELOPMENT
INNOVATIONS STUDY NUMBER: PRO 10	
FINAL PROTOCOL DATE: 6 MAY 2016	VERSION 3
Amendment Number 2:23 January 2018	

for clinical use and numerous additional agents are currently in clinical trials. Several agents that target specific genomic mutations have been approved based on improved treatment outcomes in a population of patients enriched for the specific genomic alteration (eg. crizotinib, vemurafenib, dabrafenib, ceritinib). Preliminary studies also suggest that targeting treatment toward known tumor genomic characteristics improves the chances of disease response with targeted agents. This pilot study will evaluate the preliminary antitumor activity of selected commercially available molecularly matched targeted therapies in patients who have failed first line treatment for one of the following four tumor types: (1) non-small cell lung cancer, (2) urothelial carcinoma, (3) non-colon gastrointestinal cancers, and (4) upper aerodigestive tract cancers.

#### 2. STUDY OBJECTIVES

#### 2.1 **Primary Objective**

The primary objective of this study is to:

• Determine the overall response rate (Complete Response [CR] + Partial Response [PR]) in each patient population receiving targeted therapy based on relevant genomic alterations.

#### 2.2 Secondary Objectives

The secondary objectives of this study are to:

- Evaluate the clinical benefit rate (CR + PR + stable disease [SD] ≥ 6 months) in each patient population receiving targeted therapy based on relevant genomic alterations.
- Determine the time to treatment failure (measured from the first day of treatment until the patient is removed from study for toxicity, disease progression, patient choice, or death) in each patient population receiving targeted therapy based on relevant genomic alterations.
- To determine the progression free survival (PFS) in each patient population receiving targeted therapy based on relevant genomic alterations.

#### **3. STUDY PATIENT POPULATION**

#### 3.1 Inclusion Criteria

Patients must meet the following criteria in order to be included in the research study:

 Patients with a histologically or cytologically confirmed diagnosis of one of the following tumor types whose disease has progressed following one line of standard therapy and/or for which no standard treatment is available that has been shown to prolong survival:

 a. Non-small cell lung cancer

CONFIDENTIAL	
STUDY DRUG(S): REGORAFENIB/AFATINIB/CABOZANTINIB	SARAH CANNON DEVELOPMENT
INNOVATIONS STUDY NUMBER: PRO 10	
FINAL PROTOCOL DATE: 6 MAY 2016	VERSION 3
Amendment Number 2:23 January 2018	

- b. Urothelial carcinoma
- c. Non-colon gastrointestinal cancers (including hepatobiliary, pancreatic, and gastroesophageal tumors)

d. Upper aerodigestive tract cancers (including lip, tongue, salivary gland, gum, oral cavity, mouth, tonsils, oropharynx, nasopharynx, nasal cavity, sinus, and larynx tumors)

- 2. Patients must have a predefined genomic alteration included in Table 1 that can be targeted with one of the FDA-approved targeted agents listed in Table 2. Patients with a genomic alteration that is not described in Table 1 but is covered by a targeted agent in Table 2 will also be eligible.
- 3. Patients must have measurable disease as measured by Response Evaluation Criteria in Solid Tumors (RECIST) criteria version 1.1 (Appendix E).
- 4. Patients must have an Eastern Cooperative Oncology Group (ECOG) Performance Status score of 0 or 1 (Appendix A).
- 5. Age greater than or equal to 18 years.
- 6. Adequate hematologic function defined as:
  - Absolute neutrophil count (ANC)  $\geq 1500/\mu L$
  - Platelets  $\geq$  75,000/µL
- 7. Adequate liver function defined as:
  - Alanine aminotransferase (ALT) and aspartate aminotransferase (AST)  $\leq 2.5$  x the upper limit of normal (ULN) or  $\leq 5.0$  X ULN if liver metastases present
  - Total bilirubin ≤1.5 x ULN (unless the patient has Grade 1 bilirubin elevation due to Gilbert's disease or a similar syndrome involving slow conjugation of bilirubin)
- 8. Adequate renal function defined as serum creatinine  $\leq 1.5$  x the upper limit of normal OR measured or calculated creatinine clearance  $\geq 50$  mL/min for patients with creatinine levels greater than or equal to 1.5 x the upper limit of normal.
- 9. Patients who are therapeutically treated with an agent such as warfarin or heparin will be allowed to receive either regorafenib or afatinib provided that their medication dose and INR/PTT are stable. Close monitoring is mandatory if the patient is receiving anticoagulants. If values are above the therapeutic range the anticoagulant doses should be modified and assessments should be repeated until stable. (See Exclusion Criteria 15 for anticoagulant therapy information for patients receiving cabozantinib).
- 10. Male patients with female partners of childbearing potential and women patients of childbearing potential are required to use two forms of acceptable contraception, including one barrier method, during their participation in the study and for 90 days following last dose of study drug(s). Male patients must also refrain from donating

CONFIDENTIAL	
STUDY DRUG(S): REGORAFENIB/AFATINIB/CABOZANTINIB	SARAH CANNON DEVELOPMENT
INNOVATIONS STUDY NUMBER: PRO 10	
FINAL PROTOCOL DATE: 6 MAY 2016	VERSION 3
Amendment Number 2:23 January 2018	

sperm during their participation in the study and for 90 days after the last dose of study drug (Appendix C).

- 11. Willingness and ability to comply with study and follow-up procedures.
- 12. Ability to understand the nature of this study and give written informed consent.

#### 3.2 Exclusion Criteria

Patients who meet any of the following criteria will be excluded from study entry:

- 1. Two or more prior chemotherapy regimens in the metastatic setting.
- 2. Most recent chemotherapy  $\leq$  3 weeks and > Grade 1 chemotherapy-related side effects, with the exception of neuropathy (> grade 2 excluded) and alopecia.
- 3. Use of a study drug or targeted therapy ≤21 days or 5 half-lives (whichever is shorter) prior to the first dose of study treatment. For study drugs for which 5 half-lives is ≤21 days, a minimum of 10 days between termination of the study drug and administration of study treatment is required.
- 4. Wide field radiotherapy (including therapeutic radioisotopes such as strontium 89) administered ≤28 days or limited field radiation for palliation ≤7 days prior to starting study drug or has not recovered from side effects of such therapy.
- 5. Major surgical procedures ≤28 days of beginning study drug, or minor surgical procedures ≤7 days. No waiting required following port-a-cath placement.
- 6. Previously untreated brain metastases. Patients who have received radiation or surgery for brain metastases are eligible if therapy was completed at least 2 weeks prior to study entry and there is no evidence of central nervous system disease progression, mild neurologic symptoms, and no requirement for chronic corticosteroid therapy. Enzyme-inducing anticonvulsants are contraindicated.
- 7. Pregnant or lactating
- 8. Acute or chronic liver, renal, or pancreas disease.
- Presence of active gastrointestinal disease or other condition that will interfere significantly with the absorption, distribution, metabolism, or excretion of oral therapy (e.g. ulcerative disease, uncontrolled nausea, vomiting, diarrhea Grade ≥2, and malabsorption syndrome).
- 10. Any of the following cardiac diseases currently or within the last 6 months:
  - Unstable angina pectoris
  - Congestive heart failure (New York Heart Association (NYHA) ≥ Grade 2 [Appendix B])
  - Acute myocardial infarction

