#### CONFIDENTIAL

STUDY DRUG(S): REGORAFENIB/AFATINIB/CABOZANTINIB INNOVATIONS STUDY NUMBER: PRO 10 FINAL PROTOCOL DATE: 6 MAY 2016 Amendment Number 2:23 January 2018 SARAH CANNON DEVELOPMENT

	
 
Adequate renal function defined as serum creatinine ≤1.5 x the upper limit of normal OR measured or calculated creatinine clearance ≥50 mL/min for patients with creatinine levels greater than or equal to 1.5 x the upper limit of normal.
 

	9. Patients who are therapeutically treated with an agent such as warfarin or heparin will be allowed to receive either regorafenib or afatinib, provided that their medication dose and INR/PTT are stable. Close monitoring is mandatory if the patient is receiving anticoagulants. If values are above the therapeutic range the anticoagulant doses should be modified and assessments should be repeated until stable. (See Exclusion Criteria 15 for anticoagulant therapy information for patients receiving cabozantinib).
	10. Male patients with female partners of childbearing potential and women patients of childbearing potential are required to use two forms of acceptable contraception, including one barrier method, during their participation in the study and for 90 days following last dose of study drug(s). Male patients must also refrain from donating sperm during their participation in the study and for 90 days after the last dose of study drug (Appendix C).
	11. Willingness and ability to comply with study and follow-up procedures.
	12. Ability to understand the nature of this study and give written informed consent.
Exclusion Criteria:	1. Two or more prior chemotherapy regimens in the metastatic setting.
	
 
Most recent chemotherapy ≤ 3 weeks and > Grade 1 chemotherapy-related side effects, with the exception of neuropathy (> grade 2 excluded) and alopecia.
 

	3. Use of a study drug or targeted therapy ≤21 days or 5 half-lives (whichever is shorter) prior to the first dose of study treatment. For study drugs for which 5 half-lives is ≤21 days, a minimum of 10 days between termination of the study drug and administration of study treatment is required.
	
 
Wide field radiotherapy (including therapeutic radioisotopes such as strontium 89) administered ≤28 days or limited field radiation for palliation ≤7 days prior to starting study drug or has not recovered from side effects of such therapy.
 

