#### 5.3.2 Prohibited Concomitant Medications

The following treatments are prohibited or should be used with caution while in this study:

- No other investigational therapy should be given to patients. No anticancer agents other than the study medications should be given to patients. If such agents are required for a patient, then the patient must first be withdrawn from the study.
- Herbal preparations/medications are not allowed throughout the study. These herbal medications include, but are not limited to: St. John's wort, kava, ephedra (ma huang), gingko biloba, dehydroepiandrosterone (DHEA), yohimbe, saw palmetto, and ginseng. Patients should stop using these herbal medications 7 days prior to first dose of study drug.
- Regorafenib and cabozantinib are metabolized by the cytochrome P450 (CYP) system. Therefore, drugs that are strong inducers or inhibitors of CYP3A4 should be avoided. These drugs are listed in Appendix F. Other potential drug interactions are described in the

CONFIDENTIAL	
STUDY DRUG(S): REGORAFENIB/AFATINIB/CABOZANTINIB	SARAH CANNON DEVELOPMENT
INNOVATIONS STUDY NUMBER: PRO 10	
FINAL PROTOCOL DATE: 6 MAY 2016	VERSION 3
Amendment Number 2:23 January 2018	

product package inserts for the individual agents and should be reviewed prior to the start of study treatment.

• Afatinib is a substrate of the P-glycoprotein transporter (MDR1). Caution should be exercised when combining afatinib with P-gp modulators. Below are the lists of potent P-gp inhibitors and inducers. Additional information can be found in the afatinib product package insert in Appendix H.

**Potent P-glycoprotein Inhibitors:** amiodarone, azithromycin, captopril, carvedilol, clarithromycin, conivaptan, cyclosporine, diltiazem, dronedarone, erythromycin, felodipine, itraconazole, ketoconazole, lopinavir, nelfinavir, ritonavir, quinidine, ranolazine, saquinavir, tacrolimus, ticagrelor, verapamil.

**Potent P-glycoprotein Inducers:** carbamazepine, phenytoin, rifampicin, St John's Wort, phenobarbital salt, tipranavir, ritonavir.

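### Exclusion 2 joins recent chemotherapy and residual toxicity with 'and', so read literally it sets no stand-alone chemotherapy interval and its toxicity limit lapses after 3 weeks

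*Combined protocol and SAP*

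**What the plan says.** Section 3.2 opens its list with "Patients who meet any of the following criteria will be excluded from study entry". One numbered item is therefore enough to exclude, but that item has to be met in its own terms.

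Item 2 takes the most recent chemotherapy at or under "3 weeks and > Grade 1 chemotherapy-related side effects, with the exception of neuropathy (> grade 2 excluded) and alopecia". The synopsis has the same construction, "Most recent chemotherapy ≤ 3 weeks and", followed by the same toxicity clause, so neither copy corrects the other.

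The neighbouring items are built differently:

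- Item 3 (study drug or targeted therapy) sets an interval whatever the toxicity, and for drugs with 5 half-lives of 21 days or less adds that "a minimum of 10 days between termination of the study drug and administration of study treatment is required".
- Item 4 (radiotherapy) gives time windows and then a separate ground, "or has not recovered from side effects of such therapy".
- Item 5 (surgery) sets windows alone: "28 days of beginning study drug, or minor surgical procedures" with a 7-day limit.

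Section 5.3.2 also asks for a gap before treatment for herbal products: "Patients should stop using these herbal medications 7 days prior to first dose of study drug".

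**The concern.** A washout rule usually has two jobs: to keep patients off a new agent until the last treatment has had time to act and clear, and to keep out those who have not recovered from it. Joined by 'and', item 2 does neither on its own. Recent chemotherapy alone never excludes, and unrecovered toxicity alone excludes only inside the 3-week window.

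Two groups then pass the item. Group (a) could start regorafenib, afatinib or cabozantinib days after chemotherapy, provided toxicity is Grade 1 or less. Group (b) could start with toxicity above the protocol's own Grade 1 limit, provided more than 3 weeks have passed. Both are patient-safety questions. In addition, the synopsis plans about 20 sites. If some follow the literal text and others read it as 'or', the same patient could be eligible at one site and not at another.

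**Working it through.** **The plan's own figure.** Section 10 states 40 evaluable patients per arm and at least 8 responders, for 10% against 25%, one-sided alpha 5%, power 80%. The exact binomial tail P(X ≥ 8 | n = 40, p) is 0.0419 at p = 0.10 and 0.8180 at p = 0.25, so the design reproduces. Item 2 is not an input to it.

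**Truth table for item 2.** Let A = last chemotherapy 21 days ago or less (3 × 7 = 21) and B = toxicity above Grade 1, leaving alopecia and neuropathy aside. The item names no reference date; I count days from last chemotherapy to first dose.

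| Case | 'A and B' (as written) | 'A or B' |
|---|---|---|
| ≤21 days, >Grade 1 | excluded | excluded |
| ≤21 days, ≤Grade 1 (group a) | not excluded | excluded |
| >21 days, >Grade 1 (group b) | not excluded | excluded |
| >21 days, ≤Grade 1 | not excluded | not excluded |

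The literal text excludes 1 of 4 cases and 'or' excludes 3 of 4; they differ in 3 − 1 = 2.

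**Boundary.** A Grade 2 effect on day 21 excludes under both readings. On day 22 it no longer excludes under item 2 as written, but still would under 'or'.

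**Windows that bar entry by themselves.**

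| Prior exposure | Window |
|---|---|
| Chemotherapy, item 2 literal | none |
| Chemotherapy, item 2 as 'or' | 21 days |
| Study drug or targeted therapy (item 3) | 21 days or 5 half-lives, whichever is shorter; 10-day floor for study drugs with 5 half-lives ≤21 days |
| Radiotherapy (item 4) | 28 days wide field, 7 days limited field |
| Surgery (item 5) | 28 days major, 7 days minor |
| Herbal preparations (Section 5.3.2) | 7 days |

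Chemotherapy is the only entry without a window of its own on the literal reading.

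**Does another criterion close the gap?** For an interval, no: Exclusion 1 counts regimens, and Exclusions 3 to 5 concern other treatments. For toxicity, the cover is partial:

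- Inclusion 4 requires ECOG 0 or 1; Inclusions 6–8 limit ANC, platelets, ALT/AST, bilirubin and creatinine.
- Exclusion 8 covers liver, renal and pancreas disease.
- Exclusion 9 covers conditions that interfere with oral therapy, such as "uncontrolled nausea, vomiting, diarrhea Grade ≥2, and malabsorption syndrome".
- Exclusions 10–13 cover cardiac disease, hypertension, thromboembolism and bleeding.
- Exclusion 17 covers non-healing wounds, ulcers and fractures; Exclusion 19 covers serious infection or other serious conditions.

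None is a general limit on residual chemotherapy toxicity. Grade 2 skin toxicity on day 22, in a patient with ECOG 0 or 1, is an example that could pass them all.

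**The case against.** The strongest reply is that 'and' is deliberate. Two items later the drafters wrote 'or', so they knew the difference, and item 2 may be meant to waive the wait for patients who have already recovered. That stands as a possibility for group (a), and the documents give no evidence of harm from starting these agents when chemotherapy effects are Grade 1 or less. It does not explain why the toxicity limit should disappear on day 22, so it leaves group (b) unanswered.

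The second reply is that the backstops leave little. This has force. What remains in group (b) is mainly non-serious, non-gastrointestinal toxicity in a fit patient. In group (a), Inclusion 6 with baseline laboratory tests within 7 days of treatment (Section 7.1) requires adequate neutrophils and platelets at entry. The absence of a window in item 2 is therefore a statement about that item and not a measure of actual exposure. The neuropathy parenthesis may also work as a limit of its own.

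A reader might infer more than the documents support, in three ways:

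- *That late chemotherapy effects would distort the adverse-event results.* Section 11.3.6 makes a condition present at study start an adverse event only if it worsens, so group (b)'s existing toxicity stays out of the tables otherwise. New late effects could enter the all-causality tables, but those include every cause by design. Related events are summarised separately (Section 10.2.3), with causality judged under Section 11.1.6.
- *That nobody checks washout centrally.* Section 5.1.1 describes the Medical Monitor's check of alteration and agent without saying that it is the only one. Section 4 routes registration through a central enrollment desk whose review is not described. Silence does not show that a check is absent.
- *That the operating characteristics change.* Nothing in the sample-size calculation depends on item 2.

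**Conclusion.** The point holds as an ambiguity in an operative safety criterion, probably a drafting slip. As written in both places, item 2 excludes one of the four interval-by-toxicity combinations where 'or' would exclude three, and nothing else in the protocol supplies the missing interval or a general toxicity limit.

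Confidence that 'or' was intended is moderate. It rests on Exclusion 4 and the pattern of Exclusions 3 to 5. The case is firmer for the toxicity limit, since no offered reading explains its lapse after 3 weeks, than for the interval, where a waiver is plausible.

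The consequence is patient safety and possibly uneven eligibility. Its size in patients is unknown: the documents do not say how sites read the item or how many candidates fall in either group.

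**What to change.** Have the sponsor's clinical lead confirm the intent, then reword item 2 in Section 3.2 and the synopsis, for example:

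> Last chemotherapy 3 weeks or less before the first dose of study treatment; or any unresolved side effect of chemotherapy above Grade 1 (neuropathy: above Grade 2; alopecia exempt). For ANC, platelets, ALT/AST, bilirubin and creatinine, the limits in Inclusion Criteria 6–8 apply instead.

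The last sentence stops the new text from overriding values those items expressly allow, such as raised creatinine with clearance of at least 50 mL/min. It names the tests on purpose. Exempting all laboratory values would leave haemoglobin, magnesium and electrolytes with no limit from day 22, because Inclusions 6–8 do not cover them; here they stay under the Grade 1 limit.

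If early entry of recovered patients was intended, state that waiver explicitly and still let the toxicity limit stand alone.

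The cost is a wording change in two places. Section 14.1 requires company, investigator and IRB approval of amendments, so bundle it with the next one. If sites now follow the literal text, some patients may wait longer or become ineligible.

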#### CONFIDENTIAL

STUDY DRUG(S): REGORAFENIB/AFATINIB/CABOZANTINIBSARAH CANNON DEVELOPMENTINNOVATIONS STUDY NUMBER: PRO 10FINAL PROTOCOL DATE: 6 MAY 2016VERSION 3AMENDMENT NUMBER 2:23 JANUARY 2018VERSION 3

- Conduction abnormality not controlled with pacemaker or medication
- Significant ventricular or supraventricular arrhythmias (patients with chronic ratecontrolled atrial fibrillation in the absence of other cardiac abnormalities are eligible)
- Valvular disease with significant compromise in cardiac function
- Inadequately controlled hypertension (i.e., systolic blood pressure [SBP] >180 mmHg or diastolic blood pressure (DBP) >100 mmHg) (patients with values above these levels must have their blood pressure (BP) controlled with medication prior to starting treatment).
- 12. Thrombotic, embolic, venous, or arterial events, such as cerebrovascular accident (including transient ischemic attacks) deep vein thrombosis or pulmonary embolism within 6 months of start of treatment.
- 13. Evidence or history of bleeding diathesis or coagulopathy; any haemorrhage or bleeding event  $\geq$  NCI CTCAE Grade 3 within 4 weeks prior to start of treatment.
- 14. **For patients receiving cabozantinib only**: Do not administer cabozantinib to patients that have high risk or at high risk for severe haemorrhage. Examples include:
  - a. The patient has radiographic evidence of cavitating pulmonary lesion(s).
  - b. The patient has tumor invading or encasing any major blood vessels.
  - c. The patient has had hemoptysis of  $\ge 0.5$  teaspoon (2.5ml) of red blood within 3 months before the first dose of study treatment.
  - d. The patient has experienced clinically significant GI bleeding within 6 months of the first dose of study treatment.
  - e. The patient has experienced any other signs indicative of pulmonary hemorrhage within 3 months of the first dose of study treatment.
- 15. For patients receiving cabozantinib only: Do not administer cabozantinib to patients that have high risk or at high risk of perforation or fistula:
  - a. The patient has evidence of tumor invading the GI tract, active peptic ulcer disease, inflammatory bowel disease (eg, Crohn's disease), diverticulitis, cholecystitis, symptomatic cholangitis or appendicitis, acute pancreatitis, acute obstruction of the pancreatic duct or common bile duct, or gastric outlet obstruction.
  - b. Abdominal fistula, GI perforation, bowel obstruction, or intra-abdominal abscess within 6 months before first dose.

Note: Complete healing of an intra-abdominal abscess must be confirmed before first dose.

c. The patient has pre-existing fistula of head and neck area.

 CONFIDENTIAL

 Study drug(s): Regorafenib/Afatinib/Cabozantinib
 Sarah Cannon development

 Innovations study number: PRO 10
 Final Protocol Date: 6 May 2016
 Version 3

 Amendment Number 2:23 January 2018
 Version 3

Note: Treatment areas should be healed with no sequelae from prior radiation therapy that would predispose to fistula formation.

- d. The patient has pre-existing osteonecrosis of the jaw.
- 16. Concomitant anticoagulation at therapeutic doses with oral anticoagulants (eg, warfarin, direct thrombin and Factor Xa inhibitors) or platelet inhibitors (eg, clopidogrel).
  [Patients receiving cabozantinib only]
- 17. Note: Low-dose aspirin for cardioprotection (per local applicable guidelines), low-dose warfarin (< 1 mg/day), and low dose, low molecular weight heparins (LMWH) are permitted. Anticoagulation with therapeutic doses of LMWH is allowed in subjects without radiographic evidence of brain metastasis, who are on a stable dose of LMWH for at least 12 weeks before randomization, and who have had no complications from a thromboembolic event or the anticoagulation regimen.Presence of a non-healing wound, non-healing ulcer, or bone fracture.
- 18. Patients with phaeochromocytoma.
- 19. Serious active infection at the time of treatment, or another serious underlying medical condition that would impair the ability of the patient to receive protocol treatment.
- 20. Known diagnosis of human immunodeficiency virus, hepatitis B, or hepatitis C.
- 21. Presence of other active cancers unless indolent and not requiring therapy. Patients with Stage I cancer who have received definitive local treatment and are considered unlikely to recur are eligible. All patients with previously treated in situ carcinoma (i.e., non-invasive) are eligible, as are patients with history of non-melanoma skin cancer.
- 22. Psychological, familial, sociological, or geographical conditions that do not permit compliance with the protocol.

